6.5.1 Dose Modifications for RXC004

RXC004 dose reduction and interruption are permitted.

RXC004 may be dose interrupted (withheld) until a clinically significant (any grade) and/or a grade ≥ 3 related adverse event resolves to baseline or \leq grade 2. RXC004 may also be withheld if it is necessary to give a concomitant medication that is a moderate or strong CYP3A4 inhibitor.

Colitis events may occur with RXC004 or with pembrolizumab, and should be managed per Appendix K and, for participants in Module 3, the dose modification and toxicity management guidelines for irAEs associated with pembrolizumab (Appendix L 1) if applicable. For patients receiving the combination treatment with RXC004 and pembrolizumab, the most conservative guideline should be followed.

RXC004 dose interruption and stopping criteria are detailed in Table 11.

Table 11 RXC004 Dose Modification and Stopping Criteria

Event	Action
Colitis events (e.g. Colitis, ileitis, enterocolitis etc)	
Grade 1	Reduce RXC004 to a lower dose (see Table 12 for dose reduction scheme) and manage per Appendix K. If receiving RXC004 in combination with pembrolizumab, no additional action is required for pembrolizumab.
Grade 2	Interrupt RXC004. Manage as per Appendix K. When event has resolved to Grade $\leq 1^a$ and steroids have been tapered to prednisolone ≤ 10 mg per day (or equivalent), resume RXC004 at a lower dose (see Table 12 for dose-reduction scheme). If event recurs after re-starting study treatment, then RXC004 should be permanently discontinued. If receiving RXC004 in combination with pembrolizumab, interrupt pembrolizumab and see Appendix L for guidance.
Grade 3	Interrupt RXC004. Manage as per Appendix K. When event has resolved to Grade $\leq 1^a$ and steroids have been tapered to ≤ 10 mg of prednisolone per day (or equivalent), resume RXC004 at a lower dose (see Table 12 for dose reduction scheme). If event recurs after re-starting study treatment, then RXC004 should be permanently discontinued. If receiving RXC004 in combination with pembrolizumab; permanently discontinue both agents and manage as per Appendix K and Appendix L.
Grade 4	If receiving RXC004, either as monotherapy or in combination with pembrolizumab: Permanently discontinue both agents. Manage per Appendix K and Appendix L.
Dysgeusia events	

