Grade 1/2	RXC004 related: Manage per Appendix J Consider dose reduction, depending on clinical symptoms Interrupt RXC004 treatment if dysgeusia is associated with >5 kg weight loss from baseline.

Table 11 RXC004 Dose Modification and Stopping Criteria

Event	Action
Grade 2 associated with a 10-20% decrease in body weight	RXC004 related: Manage per Appendix J Reduce RXC004 to a lower dose (see Table 12 for dose-reduction scheme).
Grade 2 associated with a > 20% decrease in body weight	RXC004 related: Permanently discontinue RXC004. If receiving RXC004 in combination with pembrolizumab, the pembrolizumab can continue if clinical benefit is judged by the Investigator.
Other AEs	
RXC004-related Grade 3 toxicity (1st event)	Interrupt RXC004 and provide supportive care, resume a lower dose level when resolved (\leq Grade 2 or returns to baseline). See Table 12 for dose-reduction scheme.
RXC004-related Grade 3 toxicity (subsequent repeat of a previously experienced event)	Permanently discontinue the related study treatment
Any Grade 4 toxicity	Permanently discontinue the study treatment.
All Grade events	Study treatment can be interrupted or discontinued for any clinically significant AEs that in the investigator's opinion warrants treatment interruption or discontinuation.
Bone events	
Confirmed (by imaging) RXC004-related fragility bone fracture (excluding grade 1 vertebral deformities)	Permanently discontinue RXC004. Pembrolizumab can continue if the patient is receiving clinical benefit as judged by the investigator.
Patients with a DEXA scan showing >7% worsening in BMD at lumbar spine or total hip compared to baseline	Permanently discontinue RXC004. Pembrolizumab can continue if the patient is receiving clinical benefit as judged by the investigator.
An individual increase in β -CTX of CCI from the baseline (screening) value or an individual measurement of CCI	Permanently discontinue RXC004 unless the patient has received clinical benefit (investigator assessment) and continued treatment is warranted. Pembrolizumab treatment can continue if the patient is receiving clinical benefit as judged by the investigator.
COVID-19 infection	
Positive COVID-19 test	Interrupt RXC004, until acute symptoms have resolved.

Table 11 RXC004 Dose Modification and Stopping Criteria

Event	Action
Major surgery	Interrupt RXC004, resume at full dose. Pembrolizumab does not need to be interrupted. No stoppage is required for biopsy procedures.

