Vomiting	If vomiting occurs shortly after RXC004 is swallowed, the dose may be replaced if all of the intact capsules can be counted. Resume with the following scheduled dose.
Missed RXC004 dose	Allowed to take the scheduled dose up to 4 hours after the scheduled dose time. If greater than 4 hours, the missed dose should not be taken and patient should continue with next dose at allotted time.

^a Attempts should be made to confirm that the colitis has resolved to Grade ≤ 1 (e.g. normalised CRP or fecal calprotectin if raised during event; GI appearance normalised on X-ray/CT or endoscopy) before restarting RXC004.

AE, adverse event; BMD, bone mineral density; COVID-19, Coronavirus disease 2019; QD, once daily.

Toxicity will be assessed using the NCI Common Terminology Criteria for Adverse Event (CTCAE) version 5.0, unless otherwise specified. Every effort should be made to administer trial treatment at the planned dose and schedule. However, patients experiencing RXC004-related toxicities may have their RXC004 dose modified as outlined below.

RXC004 related toxicities observed during the course of the study will be managed by interruption of RXC004 and initiation of appropriate treatment as judged by the Investigator. Upon re-starting treatment the guidance for dose reduction in RXC004 contained in Table 12 should be followed.

Table 12 Guidance for Dose Reductions for RXC004-related Adverse Events

Dose Level	RXC004 (Module 1 and Module 2, Cohort 1 only)	RXC004 (Module 3 only)	RXC004 (Module 2, Cohort 2 only)
Initial dose level	2 mg QD	1.5 mg QD	1 mg QD
1st dose reduction			
• Grade 3 toxicity (1 st event)	Hold RXC004 ^b . Upon resolution to ≤ Grade 2, restart at 1.5 mg QD	Hold RXC004 ^b . Upon resolution to ≤ Grade 2, restart at 1 mg QD	Hold RXC004 ^b . Upon resolution to ≤ Grade 2, restart at 0.5 mg QD
• Grade 1/2 dysgeusia ^a	Dose reduce to 1.5 mg QD	Dose reduce to 1 mg QD	Dose reduce to 0.5 mg QD
2nd dose reduction			
• Grade 3 toxicity (1 st unique event)	Hold RXC004 ^b . Upon resolution to ≤ grade 2, restart at 1 mg QD	Hold RXC004 ^b . Upon resolution to ≤ Grade 2, restart at 0.5 mg QD	Not permitted. Permanently discontinue RXC004.
• Grade 3 toxicity (recurrence of a previously experienced Grade 3 event)	Not permitted. Permanently discontinue RXC004	Not permitted. Permanently discontinue RXC004	Not permitted. Permanently discontinue RXC004

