	
Manage with corticosteroids at a dose of 1-2 mg/kg methylprednisolone equivalent.
 
When symptoms have resolved, taper over 2-4 weeks.
 
If symptoms recur during tapering, the steroid dose may need to be increased again.
 
If no improvement in 72 hrs despite treatment, treat as Grade 3.
 
RXC004 can be restarted at a lower dose after colitis has resolved to Grade $\leq 1^*$ and steroids tapered to physiological levels (<10 mg prednisolone per day equivalent dose) over at least 1 month.
 
If steroids cannot be tapered to physiological levels within 12 weeks of commencing steroid treatment, then RXC004 and pembrolizumab (if applicable) should be permanently discontinued.

Grade 3 colitis (severe or persistent abdominal pain, fever, ileus; peritoneal signs)	
Pause RXC004 and pembrolizumab, if applicable.
 
Seek specialist advice.
 
Manage with corticosteroids at a dose of 1-2 mg/kg methlyprednisolone equivalent.
 
When symptoms improve, taper steroids to physiological levels over 4-8 weeks and consider use of prophylactic antibiotics and anti-fungals.
 
RXC004 can be restarted at a lower dose after colitis has resolved to Grade $\leq 1^*$ and steroids tapered to physiological levels

Event and grade	Management
	
(<10 mg prednisolone per day equivalent dose)
 
If steroids cannot be tapered to physiological levels within 12 weeks of commencing steroid treatment, then RXC004 and pembrolizumab, if applicable, should be permanently discontinued
 
Additional anti-inflammatory medications (e.g. infliximab) may be indicated if no improvement in 48-72 hrs. It is important to rule out bowel perforation and refer to infliximab SMPC/USPI for general guidance before using infliximab.
 
If anti-inflammatories are required RXC004 and pembrolizumab, if applicable, should be permanently discontinued.

Grade 4 colitis (life-threatening consequences)	
Manage as Grade 3 colitis.
 
RXC004 and pembrolizumab, if applicable, should be permanently discontinued.

*Attempts should be made to confirm that the colitis has resolved to Grade ≤ 1 (e.g. normalised CRP or fecal calprotectin if raised during event; GI appearance normalised on X ray/ CT or endoscopy) before restarting RXC004.

If there is any recurrence of colitis \geq Grade 2 after recommencing RXC004, **RXC004 and pembrolizumab, if applicable, should be permanently discontinued.**

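### The conditions for restarting RXC004 after colitis do not agree across Section 6.5.1, Table 11, Table 12 and Appendix K, and need to be reconciled

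*Protocol*

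**What the plan says.** All references are to the protocol.

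- **Section 6.5.1, opening text.** RXC004 may be withheld for a related event of Grade 3 or higher until it returns to baseline or Grade 2 or lower. This sentence makes no exception for colitis. The next paragraph sends colitis to Appendix K and, for combination patients only, asks for the stricter guideline. Interruption and stopping criteria are assigned to Table 11.
- **Table 11, colitis block.** For Grade 2 colitis, and for Grade 3 colitis on monotherapy, restart needs Grade 1 or lower and prednisolone at 10 mg/day or less. The Grade 2 row then says "resume RXC004 at a lower dose (see Table 12 for dose-reduction scheme"; the Grade 3 row has the same pointer. A footnote adds "Attempts should be made to confirm that the colitis has resolved to Grade" 1 or lower before restart.
- **Text above Table 12.** "Upon re-starting treatment the guidance for dose reduction in RXC004 contained in Table 12 should be followed".
- **Table 12, first Grade 3 event.** For Module 1 and Module 2 Cohort 1: "Upon resolution to ≤ Grade 2, restart at 1.5 mg QD". For Module 2 Cohort 2: "Upon resolution to ≤ Grade 2, restart at 0.5 mg QD". A recurrent Grade 3 event means permanent discontinuation in every column.
- **Appendix K, Table 19.** Restart after Grade 2 or Grade 3 colitis needs Grade 1 or lower and steroids at physiological levels, given as "<10 mg prednisolone per day equivalent dose". "If steroids cannot be tapered to physiological levels within 12 weeks of commencing steroid treatment", RXC004 is stopped permanently.
- **Section 5.6.3.1.** Steroids given for study-drug adverse events are to be down to 10 mg/day or less before restart.
- **Table 11, major surgery.** "Interrupt RXC004, resume at full dose".

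**The concern.** A site handling a first Grade 3 colitis event reads the Table 11 row, follows its pointer to Table 12, and finds a cell stating a different resolution grade and no steroid condition. The general sentence that opens Section 6.5.1 agrees with Table 12 and not with the colitis row. The two colitis-specific sources also differ from each other on the steroid level.

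Patient safety is the first matter at stake. Colitis is a designated adverse event of potential interest for RXC004 (Section 8.3.13), and three of the four Phase 1 patients with intestinal inflammation had it as a dose-limiting toxicity (Section 2.3.1.2). It is one of several such toxicities: Table 1 records a pancreatitis and Table 5 a drug-induced liver injury. The second matter is reporting. Dose reductions, interruptions and discontinuations are a stated safety endpoint (Section 3) and are tabulated under SAP Sections 4.10 and 4.12.1, so different site readings would pass into the results.

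**Working it through.** The plan states no figure to reproduce. The check sets the rules side by side and then sizes the setting.

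**Step 1. Restart after a first Grade 3 colitis, monotherapy (Modules 1 and 2).**

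| Source | Resolution needed | Steroid condition | Colitis named? |
|---|---|---|---|
| 6.5.1 opening sentence | baseline or Grade 2 or lower | none | no |
| Table 12, first-event Grade 3 row | Grade 2 or lower | none | no |
| Table 11, Grade 3 colitis row | Grade 1 or lower | 10 mg/day or less | yes |
| Appendix K, Grade 3 | Grade 1 or lower | below 10 mg/day | yes |

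Take a patient whose Grade 3 colitis has improved to Grade 2. Table 12 read alone gives restart one dose level down. Table 11 and Appendix K both give continued hold. If that patient were restarted, the Table 11 Grade 2 colitis row would call for interruption straight away.

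**Step 2. Where the mismatch stops.**

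- Grade 1 or Grade 2 colitis: Table 12 has no row for these, so it states no competing grade.
- Recurrent Grade 3 colitis: Tables 11 and 12 and Appendix K all discontinue.
- Other Grade 3 events: the Other AEs block of Table 11 and Table 12 both use Grade 2 or lower.
- Module 3: Table 11 permanently discontinues both agents at Grade 3 colitis, and the stricter-guideline sentence applies.

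What remains is a first, non-recurrent Grade 3 colitis on monotherapy.

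**Step 3. Steroid level.** Suppose colitis is at Grade 1 or lower.

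| Daily prednisolone equivalent | Table 11 and 5.6.3.1 | Appendix K |
|---|---|---|
| below 10 mg | restart allowed | restart allowed |
| exactly 10 mg, before 12 weeks | restart allowed | hold |
| exactly 10 mg, at 12 weeks | restart allowed | permanent discontinuation |
| above 10 mg | hold | hold; permanent discontinuation at 12 weeks |

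The two middle rows differ at a single value, but both rules compared are colitis rules. Preferring the specific rule to the general one therefore does not settle them.

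**Step 4. How often the setting arises.** Section 2.3.1.2 reports one Grade 3 colitis SAE among 21 patients dosed in this study, at 2 mg QD: 1/21 = 4.8%. The exact 95% limits are 1 − 0.975^(1/21) = 0.1% and the p solving (1 − p)^21 + 21p(1 − p)^20 = 0.025, which is 23.8%. The sister study RXC004/0002 reports one Grade 3 enteritis among 12: 1/12 = 8.3%. That study runs under its own protocol and is context only.

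**Step 5. Effect on the tabulated safety data.** Under either reading, a patient restarted after a first Grade 3 colitis has been interrupted and then reduced. The numbers of patients with an interruption and with a reduction do not change for that event. The length of the hold can change, as can any later interruption or discontinuation. SAP Section 4.10 divides cumulative dose by days from first to last dose times the planned dose, so hold days stay in the denominator and a longer hold lowers relative dose intensity.

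**The case against.** The strongest reply is that the protocol already assigns the roles. Section 6.5.1 gives interruption criteria to Table 11 and colitis management to Appendix K, and both use Grade 1. Table 11 separates colitis from other adverse events, and Table 12 mirrors the rule for the latter. The colitis rows cite Table 12 for the reduction scheme only, and do so even for Grades 1 and 2, where Table 12 has no row; it is serving as a dose ladder. This largely stands as the likelier intended reading. It does not remove the point, because the cell reached through the cross-reference states a contrary condition, no passage says the colitis rows override it, and the tie-breaker leaves out monotherapy patients.

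Several stronger readings are tempting, and the documents do not support them:

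- *That Table 12 restarts after any Grade 3 toxicity.* Recurrences are discontinued, and so is a second distinct Grade 3 event in Module 2 Cohort 2.
- *That "Upon re-starting treatment the guidance for dose reduction in RXC004 contained in Table 12 should be followed" makes Table 12 binding on when to restart.* The sentence concerns the dose once treatment restarts.
- *That "Interrupt RXC004, resume at full dose" reverses an earlier toxicity reduction.* Its natural sense is that surgery alone triggers no reduction. No passage provides for re-escalation, and Section 8.4 counts any dose above the assigned daily dose as an overdose. The row is merely silent on patients already reduced.
- *That the two studies can be pooled as 2/33 to size the problem here.* This protocol governs only the 21.

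On steroids, the reply is that the Table 11 colitis rows invoke Appendix K and so import its 12-week rule. That is fair, but the same rows state a different limit from the appendix they invoke.

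**Conclusion.** The point holds as an internal inconsistency of limited reach.

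1. For a first Grade 3 colitis on monotherapy, the stated restart grade differs by one CTCAE grade between the colitis rules and the Table 12 cells and opening text of Section 6.5.1, and the latter two omit the steroid condition.
2. The steroid level differs between Appendix K and both Table 11 and Section 5.6.3.1, with opposite actions at exactly 10 mg/day.
3. As a minor matter, full dose after surgery is undefined for a patient already reduced.

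A reader might infer that sites are offered two equally valid rules, or that the counts of patients interrupted and reduced would shift materially. Neither follows: the text leans towards the colitis rows, and for the index event those counts are the same under both readings. The setting is nonetheless real, with one Grade 3 colitis in 21 patients in this study, a rate that is imprecisely estimated. How often sites would actually diverge cannot be found from the documents. Nothing here bears on which grade or steroid level is clinically right.

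**What to change.** At the next amendment:

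- State in Table 12, and in the opening text of Section 6.5.1, whether the Grade 3 restart condition applies to colitis events or whether Table 11 and Appendix K govern them.
- Use one steroid limit in Table 11, Section 5.6.3.1 and Appendix K, and tie the 12-week rule to the same limit.
- In the major-surgery row, say what full dose means for a patient already dose-reduced.

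The sponsor's clinical team should choose the thresholds. The cost is wording in these passages and a notice to sites, with no extra patients, visits or procedures.

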6.6 Access to Study Treatment after the End of the Study

Any patients still receiving investigational product at the time of the data cut off will be able to continue to receive investigational products within the current study while in the Investigator's opinion, deriving clinical benefits and not fulfilling the discontinuation criteria.

In Module 3, for those patients who are continuing on combination therapy with RXC004 and pembrolizumab, both agents can be administered until discontinuation criteria are met.

Patients who discontinue RXC004 may continue to receive pembrolizumab q6w alone. The continued access to pembrolizumab will end when a criterion for discontinuation is met or 18 doses of pembrolizumab (q6w dosing) have been administered (approximately 2 years), whichever is sooner.

Assessments will revert to standard of care for each individual site.

In Modules 1 and 2, patients will continue to be monitored for all SAEs up to 30 (+3) days after the last dose of RXC004 (i.e. patients treated with RXC004 monotherapy only).

In Module 3, patients will continue to be monitored for all AEs and Events of Clinical Interest for pembrolizumab up to 30 (+3) days after the last dose of RXC004 or pembrolizumab.

Follow-up for SAEs will continue for 30 (+3) days after the last dose of RXC004 and for 90 days after the last dose of pembrolizumab.

A paper form process will be used for AE, Events of Clinical Interest, and SAE reporting. All SAEs and overdoses will be reported until 30 days after last dose of RXC004 (Modules 1 and 2) or 90 days after the last dose of pembrolizumab (Module 3). All pregnancies will be reported up to 5 months after the last dose of the study drug(s).

The investigational product will be supplied to sites manually. The investigational product dispensation and reconciliation will be handled by the study team at each patient's visit. The investigational product accountability information must still be collected until all patients have completed treatment.

7 DISCONTINUATION OF STUDY TREATMENT AND PARTICIPANT DISCONTINUATION/WITHDRAWAL

7.1 Discontinuation of Study Treatment

An individual patient will not receive any further IP if any of the following occur:

- Patient decision to withdraw from further treatment with IP. The patient is, at any time, free to discontinue treatment, without prejudice to further treatment.
- Clinical or RECIST 1.1-defined radiological progression. (Symptomatically/clinically

stable patients may continue treatment until symptomatic/clinical progression or second RECIST 1.1 progression [relative to the first ‘on study treatment’ RECIST 1.1 progression]. See Section 7.1.1 for details for continuing study treatment after RECIST1.1 defined progression.

- An AE that meets RXC004 discontinuation criteria in Table 11.
- Pregnancy or intent to become pregnant.
- Initiation of alternative anticancer therapy including another investigational agent .
- Non-compliance with the study protocol that, in the opinion of the Investigator or Sponsor, warrants withdrawal from treatment with IP.

For participants in Module 3 (RXC004 in combination with pembrolizumab), the following additional criteria for discontinuation of pembrolizumab apply:

- Completion of 18 administrations (approximately 2 years) with pembrolizumab (q6w dosing). [Note: The number of administrations is calculated starting with the first dose of pembrolizumab.]
- Any study intervention-related toxicity specified as a reason for permanent discontinuation of pembrolizumab as defined in the guidelines for dose modification due to AEs in Appendix L.
- Discontinuation of treatment may also be considered for participants who have attained a confirmed complete response (CR) and have been treated for at least 24 weeks, receiving at least 2 doses of pembrolizumab beyond the date when the initial CR was declared.

Discontinuation from study treatment is NOT the same thing as a withdrawal from the study. If study treatment is permanently discontinued, the participant will remain in the study to be evaluated for safety, progression (if the patient discontinues for a reason other than progression) and survival. See the Schedule of Assessments (Table 15, Table 16, and Table 18) for data to be collected at the time of discontinuation of study treatment and during follow-up.

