8.1 Efficacy Assessments

The following efficacy assessments will be conducted for each patient in this study – PFS, objective response (CR, PR, SD or PD), [REDACTED], % change in the sum of target lesions and OS. The primary and secondary endpoints for each module are specified in Section 3.

Efficacy assessments other than OS will be derived using investigator RECIST 1.1 assessments.

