8.1.1 Tumour Assessments

Tumour assessments use images from CT or MRI, collected during screening/baseline and at regular (follow-up) intervals during the study. The same imaging method should be used throughout the study. It is important to follow the tumour assessment schedule as per the SoA. Tumour assessments will continue until RECIST1.1-defined radiological progression. Scan timing should follow calendar days and should not be adjusted for delays in cycle starts.

Sites will be required to store electronic copies of all scans until study closure, and the Sponsor may arrange for possible centralised storage of all anonymised imaging data. Centralised storage of imaging data would be possible to support an independent centralised review of disease assessments.

In addition, if available, the last 2 imaging scans taken prior to the screening scan for this study and/or their reports should be kept for possible central/sponsor review.

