10.8.1 Schedule of Assessments

Table 15 Module 1 (PDAC) Schedule of Assessments

	Module 1 (PDAC)– Schedule of assessments						
	Pre-Screening ^t	Screening	Cycle 0 (3-7 days)	Cycle 1 (21-day cycle)	IP Discontinuation	30 day follow-up	Survival follow-up
Window	n/a	-28 to -1	D1	D15 ± 1d	Within 7 days of discontinuation	± 3d	q6w ± 1 week
Pre-Screening informed consent							
CC1 [REDACTED] CC1	X						
Genetic screening for RNF43 mutations	X						
Main study informed consent							
Demography & baseline characteristics		X					
Tumour genetic and PD-L1 staining history (optional)			X				
CC1 [REDACTED] CC1				X			
(optional and only applicable if not previously collected during central pre-screening)							
Substance use (smoking and alcohol)			X				

Module 1 (PDAC)– Schedule of assessments							
	Pre-Screening ^t	Screening	Cycle 0 (3-7 days)	Cycle 1 (21-day cycle)	Cycle X Day 1 (21-day cycle)	IP Discontinuation	30 day follow-up
Window	n/a	-28 to -1	D1	D1 ± 1d	± 3d	Within 7 days of discontinuation	± 3d q6w ± 1 week
Medical/surgical history		X					
Oral and dental assessments ^o		X					
Inclusion/exclusion criteria ^u		X					
CCI		X					
CCI							
CCI							
CCI							
Physical examination		X	X	X	X	X	X
Karnofsky performance status		X	X	X	X	X	X
Pregnancy test (WOOCBP only)		(X)	(X)	(X)	(X)		
Baseline and 'on treatment' tumour biopsies (mandatory) ^a		X			X ^g		X (optional at progression)
Vital signs (including height and weight) ^m		X	X	X	X	X	X
Clinical chemistry / Haematology		X	X	X	X	X	X

Module 1 (PDAC)– Schedule of assessments							
	Pre-Screening ^t	Screening	Cycle 0 (3-7 days)	Cycle 1 (21-day cycle)	Cycle X Day 1 (21-day cycle)	IP Discontinuation	30 day follow-up
Window	n/a	-28 to -1	D1	D1 ± 1d	± 3d	Within 7 days of discontinuation	± 3d
ECG^w		X	X	X	X	X	X
Blood samples for bone turnover biomarkers (β-CTX)		X		X	X ^k		
DEXA scan		X			X ^l		
CC1			X		X		
CC1							
CC1				X	X		
CC1					X		
CC1						Cycle 2 only	
CC1				X	X		
CC1					X	X	X
RXC004 PK ^f			X		X		
RECIST 1.1 assessments (CT or MRI) ^j		X				On study tumour assessments should occur q6w ± 1 week (relative to first dose of IP) for the first 54 weeks, followed by q12w ± 1 week until RECIST 1.1 radiological progression ⁿ	
CC1 (mandatory unless unavailable at site) ^p		X				On study CC1 assessment should occur at week 6 ± 1 week and week 18 ± 1 week relative to first dose of IP.	

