### 3.2.1.1 Progression Free Survival

PFS is defined as the time from first dose of study treatment (C0D1) until the date of disease progression or death (by any cause in the absence of progression), regardless of whether the patient withdraws from the assigned study treatment or receives another anticancer treatment prior to progression.

Patients who have not progressed or died at the time of analysis will be censored at the time of the latest date of RECIST 1.1 assessment of their last evaluable scan, however if the patient progresses or dies after 2 or more missed scheduled scanning visits (Progression/Death date - Last available scan date $\geq$ 12 +1 weeks), the patient will be censored at the time of their last evaluable scan prior to the missing scan visits. If the patient has no evaluable visits or does not have baseline data, they will be censored at 0 days. However, if the patient dies within 2 scan visits of first dose (within 12 + 1 weeks from first dose date without a post baseline scan) then its death date will be treated as their progression date. Progression free survival rate at 6 months is the primary endpoint. PFS time is defined as:

$$\text{PFS (days)} = \text{Date of documented PD, Death or last RECIST 1.1 assessment} - \text{first dose of study treatment (C0D1)} + 1$$

Progression free survival rate at 6 months will be defined as the proportion of patients alive and progression free at 6 months.

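### Protocol 7.1 can be read as ending RECIST follow-up after clinical progression, contrary to 8.1.1 and the schedules, and the SAP gives no clear PFS rule for such patients

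*Protocol*

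**What the plan says.** **Protocol 7.1** gives as one reason for stopping treatment: "Clinical or RECIST 1.1-defined radiological progression". After stopping, the patient stays in the study to be evaluated for safety, "progression (if the patient discontinues for a reason other than progression) and survival". The same paragraph refers onward: "See the Schedule of Assessments (Table 15, Table 16, and Table 18) for data to be collected".

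**Protocol 8.1.1** says: "Tumour assessments will continue until RECIST1.1-defined radiological progression". The Module 1 schedule (10.8.1) asks for six-weekly scans "for the first 54 weeks, followed by q12w ± 1 week until RECIST 1.1 radiological progression", and the Module 2 schedule (11.8.1) has the same rule. Sections 4.1, 10.5, 11.5 and 12.5 move patients to safety and survival follow-up only after radiological progression.

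**Endpoint derivation.** Protocol 8.1 says: "Efficacy assessments other than OS will be derived using investigator RECIST 1.1 assessments". SAP 3.2.1.1 runs PFS to progression or death, "regardless of whether the patient withdraws from the assigned study treatment or receives another anticancer treatment prior to progression". A progression or death 13 weeks (12 + 1) or more after the last scan is censored back to that scan. "If the patient has no evaluable visits or does not have baseline data, they will be censored at 0 days", except that a death within 13 weeks of first dose, with no post-baseline scan, is an event. SAP 3.2.1.2 uses only the investigator's overall response at RECIST visits. The closing paragraph of the SAP appendix (5.1.4) nevertheless says that PD may also be a worsening of the patient's condition or symptoms.

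**The concern.** Two questions are left open, and both bear on the primary endpoint of Modules 1 and 2.

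The first is who is scanned. Clinical progression is a stopping reason in 7.1, and the follow-up clause a few lines later says only progression, without the RECIST qualifier that the protocol uses elsewhere. Section 8.3.7 describes disease progression as including an increase in symptoms. A site can therefore reasonably conclude that a patient who stops for clinical progression needs no more scans, while 8.1.1 and the schedules say the opposite.

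The second is how the patient is coded. For clinical progression without RECIST PD, the body of the SAP points to censoring and its appendix can be read as allowing an event. Two analysts could code the same patient differently.

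If scanning did stop, the patients censored would be those judged to be failing. That censoring is informative, and it pushes the Kaplan-Meier estimate up. In a single-arm comparison with a fixed benchmark, no control arm shares the bias.

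**Working it through.** **The plan's own figures.** The stated error rates are 0.06 and 0.10 (Module 1) and 0.06 and 0.20 (Module 2). They cannot be reproduced because the sample sizes, cut-offs, p0 and p1 are redacted. A coarse grid (n from 10 to 40, rates in steps of 0.05) finds Module 1 designs at n = 15, 24 and 26, so the design is not identifiable. This point does not dispute the error rates.

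**What the censoring rule does.** Take a patient whose last scan is 42 days after first dose and who then leaves scanning for clinical progression. The limit is 42 + 91 = 133 days. Death before day 133 is an event; death later, or no death, is censored at day 42. With no post-baseline scan, death within 91 days is an event; otherwise the patient is censored at day 0 and contributes nothing to the curve.

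**Inputs from the documents.**
- Reference medians for pancreatic cancer: PFS 3.1 and OS 6.2 months (Protocol 10.3.2).
- Reference medians for biliary cancer: PFS 4 months (11.5.1) and OS 6.2 months (11.3.2).
- Scans every 42 days; one month is 30.4375 days (SAP 4.11.2.1), so six months is 182.6 days.

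**Assumptions.**
- Exponential times.
- Median survival after progression taken as OS minus PFS: 6.2 − 3.1 = 3.1 months (pancreatic) and 6.2 − 4.0 = 2.2 months (biliary).
- Share of progressions that are clinical only: 10–40%. The documents give no figure.

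**Baseline check.** True 6-month PFS is 0.5^(6/3.1) = 26.1% and 0.5^(6/4) = 35.4%. The last scan before 182.6 days is at 168 days, or 5.52 months, so with full scanning the Kaplan-Meier value should be near 0.5^(5.52/3.1) = 29.1% and 0.5^(5.52/4) = 38.4%. Simulation gives about 29% and 38%.

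**Kaplan-Meier 6-month PFS, 60,000 simulated patients per scenario.** The standard error is about √(0.29 × 0.71 / 60,000) = 0.2 points.

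| Clinical-only share | 10% | 20% | 30% | 40% |
|---|---|---|---|---|
| Pancreatic, all scanned to RECIST PD or death | 28.9 | 28.9 | 28.7 | 28.9 |
| Pancreatic, all clinical-only leave scanning | 31.0 | 33.2 | 35.5 | 38.2 |
| Pancreatic, half leave | 30.3 | 31.0 | 32.3 | 33.5 |
| Biliary, all scanned to RECIST PD or death | 38.2 | 38.2 | 38.4 | 37.9 |
| Biliary, all clinical-only leave scanning | 40.0 | 42.0 | 44.1 | 45.8 |
| Biliary, half leave | 39.3 | 39.9 | 40.9 | 41.8 |

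If all leave, the excess is 2.1 to 9.3 points (pancreatic) and 1.8 to 7.9 points (biliary). If half leave, it is 1.4 to 4.6 and 1.1 to 3.9 points. Among clinical-only progressors who leave, about 40% (pancreatic) and 50% (biliary) die within 13 weeks of the last scan and remain events.

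**A second set of assumptions.** With true 6-month PFS of 20%, clinical-only share 10–30% and post-progression median survival of 2–4 months, the rate is 22.5% with full scanning and 24.0–29.6% if scanning stops, an excess of 1.5 to 7.1 points. At a true 30% it is 32.8% against 34.5–40.5%.

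**Other handling of the same patients.** Counting clinical progression as an event on its date gives 27.9–28.7% and 36.9–37.9%. Counting patients known to be progression-free past six months over all treated gives 27.8–28.6% and 37.3–38.0%. Neither is inflated.

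**The case against.** The strongest reply is that scanning to RECIST PD is already required. The wording at issue is a parenthesis in a summary sentence, the next sentence sends the reader to the schedules, and 8.1.1 and the design sections agree with the schedules. Section 8.3.7.1 also keeps imaging at the planned times when biliary obstruction occurs. This stands. A reader might infer that clinically progressing patients do leave scanning and that the 6-month rate is therefore inflated. The documents do not support that; they show a conflict between clauses, and the bias follows only where a site takes 7.1 at its word.

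A reader might also infer that all such patients are censored. They are not: early deaths are events, and the SAP appendix may let clinical worsening count as PD.

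A third inference is that the plan leans toward a go decision. SAP 3.2.1.1 defines the endpoint as a proportion, and Protocol 10.9.1 and 11.9.1 word the no-go rule as a count of progression-free patients. A patient lost early does not add to that count if kept in the denominator. Whether such patients are kept depends on an evaluable-set definition that is redacted, as are the hurdles. The reply does not remove the concern about the estimate, however. Protocol 9.4.2.2 identifies the 6-month PFS estimate as the primary endpoint directly after describing the Kaplan-Meier analysis, and SAP 4.11.2.1 specifies only Kaplan-Meier rates.

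**Conclusion.** The point holds as a conflict that needs resolving, with a conditional bias. Protocol 7.1 disagrees with 8.1.1 and the schedules on follow-up after clinical progression, and the SAP does not say clearly how such a patient enters PFS.

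If 7.1 is followed literally, the Kaplan-Meier 6-month PFS rate is biased upward by about 1.5 to 9 points, assuming a clinical-only share of 10–40% and that all such patients leave scanning. It is roughly half that if half continue, and nil if 8.1.1 and the schedules are followed. The size rests on the assumed share, exponential times and the approximate post-progression survival. The direction rests only on failing patients being censored under Kaplan-Meier.

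The rate is primary in Modules 1 and 2. In Module 3 the primary endpoint is ORR, so only secondary PFS is affected. No effect on the go/no-go decision is shown.

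**What to change.** 1. In Protocol 7.1, limit the exception to patients who stop for RECIST 1.1-defined radiological progression, so that follow-up matches 8.1.1 and the schedules. The treatment-stopping rule itself is not touched.
2. In SAP 3.2.1.1, state that the primary PFS analysis counts RECIST PD or death, and reconcile the closing paragraph of the appendix with it.
3. Add one sensitivity analysis of 6-month PFS for Modules 1 and 2 that counts discontinuation for clinical progression without later RECIST PD as an event at the discontinuation date, and report how many patients this concerns.

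The cost is one protocol clause, a short SAP edit and one extra Kaplan-Meier run. No new scans are added, because 8.1.1 and the schedules already require them. SAP 4.4 already reports the primary reason for end of treatment and the last-dose date. The readable text does not show whether the form separates clinical from radiological progression; if it does not, the split can be made by checking for a recorded RECIST PD. Some deteriorating patients will decline scans whatever the wording, which is why the sensitivity analysis is still worth having after the clause is corrected.
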